5.4 Treatment Compliance

Subjects are required to return all unused and used run-in product, IP, and study-provided AT. The materials returned will provide evidence of compliance.

5.5 Concomitant Therapy

For this protocol, a prescription medication is defined as a medication that can be prescribed only by a properly authorized/licensed clinician. Medications to be reported in the electronic case report form (eCRF) are concomitant prescription medications, over-the-counter medications, and supplements.

All medications that the subject has taken 45 days prior to Visit 1 and through Visit 6 or discontinuation from the study will be recorded in the eCRF and the subject chart. The generic name of the drug, dose, route of administration, duration of treatment (including start and stop dates), frequency, indication, and whether or not the medication was taken due to an AE will be recorded for each medication. Prior and concomitant medications (CMs) will be coded using the World Health Organization Drug Dictionary (WHODrug).

5.5.1 Prohibited Medications and Procedures

Prohibited medications and procedures that require a washout are also restricted throughout the study, unless otherwise noted.

Medication and Procedures Not Permitted	Minimum Washout Prior to Visit 1 (Unless Otherwise Noted)
Isotretinoin (Accutane)	Prior history
Corneal refractive surgery, glaucoma surgery, or corneal transplantation	2 years
Altered use of nutraceuticals or multivitamins	Throughout study
Topical ophthalmic medications, including ocular hypotensive (glaucoma) medications, eye drops, gels, or AT (other than study-provided Refresh Plus®)	Throughout study
[REDACTED]	Throughout study

Penetrating intraocular surgery	12 months
Eyelid surgery or ocular surface surgery	6 months
[REDACTED]	3 months

 • [REDACTED] • [REDACTED] • [REDACTED] • [REDACTED] • [REDACTED] • [REDACTED] 	
In either eye, have had punctal occlusion (cauterization or plugs [silicone or dissolvable]) or anticipate new or additional punctal occlusion during the duration of the study. NOTE: Permanent plugs lost should be replaced.	3 months
Any other IP	45 days
Prescription treatments for ocular surface disease, including 
 • Topical cyclosporine (Restasis®, Cequa®) • Topical lifitegrast (Xiidra®) • Ocular corticosteroids, including but not limited to fluorometholone and loteprednol etabonate (Eysuvis®) • Varenicline (Tyvara®) 	30 days
Autologous serum	30 days
Altered dose of tetracycline compounds (tetracycline, doxycycline, or minocycline). Dose must remain stable throughout study.	30 days
Contact lenses	14 days
Topical ocular antibiotics Topical ocular antihistamines or mast cell stabilizers Topical or nasal vasoconstrictors	14 days
[REDACTED]	

5.5.2 Artificial Tears

AT, whether subject- or study-supplied, is prohibited during the run-in period of the study (Visit 1 to Visit 2). Any subject who violates this policy will not be randomized to treatment and will be discontinued from the study.

Preservative-free AT (Refresh Plus[®]) will be provided for rescue use during the treatment phase of the study (Visits 2 through 6) but limited to ≤ 2 instillations per day. Subjects will be required to record AT use in a diary and return the used and unused AT at clinic Visits 2 through 6; subjects will be queried about AT use at each clinic visit.

6. Study Discontinuation/Participant Withdrawal

6.1 Discontinuation of Study Treatment or Intervention

The study IP may be discontinued by a subject at any time, although every effort will be made to ensure consistent subject participation over the 60-day treatment period. In the event of discontinuation of IP by a subject, the Investigator will make every attempt to have the subject complete Visit 6 assessments as soon as possible. The subject will be discontinued following those assessments, and the reason for premature discontinuation will be recorded in the subject chart and entered in the eCRF.

6.2 Participant Discontinuation/Withdrawal from the Study

Subjects are free to withdraw from participation in the study at any time upon request. An Investigator may discontinue or withdraw a subject from the study for the following reasons:

- Withdrawal of consent
- Study terminated by the Sponsor
- Lost to follow-up
- Pregnancy
- Significant study treatment/intervention non-compliance
- If any clinical adverse event, laboratory abnormality, or other medical condition or situation occurs such that continued participation in the study would not be in the best interest of the subject
- Disease progression that requires discontinuation of the study intervention
- If the subject meets an exclusion criterion (either newly developed or not previously recognized) that precludes further study participation

The reason for subject discontinuation or withdrawal from the study will be recorded on the eCRF. Subjects who sign the informed consent form (ICF) and are randomized but do not receive the study intervention may be replaced.

Those who sign the ICF, are randomized, receive the study treatment/intervention, and subsequently withdraw, or are withdrawn or discontinued from the study, will not be replaced.

In the event of study discontinuation, the Investigator will make every attempt to have the subject complete Visit 6 assessments as soon as possible. The reason for premature discontinuation will be recorded in the subject chart and entered in the eCRF.

6.3 Lost to Follow-Up

A subject will be considered lost to follow-up if he or she fails to return for a scheduled visit and is unable to be contacted by the study site staff.

The following actions must be taken if a subject fails to return for a required clinic study visit:

- The site will attempt to contact the subject and reschedule the missed visit within 1 week, counsel the subject on the importance of maintaining the assigned visit schedule, and ascertain if the subject wishes to and/or should continue in the study.
- Before a subject is deemed lost to follow-up, the Investigator or designee will make every effort to regain contact with the subject (where possible, 3 telephone calls and, if necessary, a certified letter to the subject's last known mailing address or local equivalent methods). These contact attempts will be documented in the subject's medical record or study file.

Should the subject continue to be unreachable, he or she will be considered to have withdrawn from the study with a primary reason of lost to follow-up.

7. Study Procedures

Written informed consent and Health Insurance Portability and Accountability Act (HIPAA) authorization will be obtained from all subjects prior to any study-related procedures being performed. The Schedule of Procedures and Assessments ([Appendix 1](#)) lists the procedures that should occur at each study visit.

7.1 Visit Descriptions

7.1.1 Screening (Visit 1, -14 days)

Ocular assessments and procedures must be performed in the order specified below. Tasks marked with an asterisk may be performed at any point (at Visit 1, after the consent is signed).

- Explain the purpose and conduct of the study to the subject, answer the subject's questions, and obtain written informed consent and HIPAA authorization.
- Assign Subject Identification Number.
- Obtain information including: demographics, CMs, ocular and systemic medical and medication history and surgical history.
- Determine study eligibility based on Inclusion/Exclusion criteria.
- Administer the following subject-rated symptom assessments:
 - Urine pregnancy test (UPT) for WOCBP*
 - Safety labs: blood samples for chemistry and hematology*
 - BCVA
- Biomicroscopy and external eye exam
- OU tear collection under slit lamp for biomarker test (quantitative point-of-care [POC] MMP-9 test by Seinda Biomedical Corp.)
- CFS
 - **Note:** After CFS grading, wait at least 15 minutes before conducting
- IOP
- Dilated ophthalmoscopy
- Enter subject information into EDC to determine the single-masked run-in kit number.
- Dispense 3 kits of single-masked run-in product (sufficient for up to 15 days) and explain the method of run-in administration.

- Observe as the subject self-administers the first dose (1 drop OU) of single-masked run-in at the clinic. All remaining doses (1 drop OU BID) will be administered by the subject at home.
- Assess for AEs.
- Remind subject:
 - Use of AT during the run-in period is prohibited. Use will result in subject's discontinuation from the study.
 - Run-in product should be administered as 1 drop OU once in the morning and once in the evening, 8-12 hours apart. **Do not dose run-in product the day of Visit 2.**
 - Return all used and unused run-in product at Visit 2.

7.1.2 Randomization (Visit 2, Day 1)

The following procedures will be performed at Visit 2:

- Confirm study eligibility based on Inclusion/Exclusion criteria.
- Update CMs
- Assess AEs
- Administer the following subject-rated symptom assessments:
 - BCVA
 -
 - Biomicroscopy and external eye exam
 - OU tear collection under slit lamp for biomarker test (quantitative POC MMP-9)
 - CFS
 - **Note:** After CFS grading, wait at least 15 minutes before conducting
 -
 - IOP
 - Confirm that the subject is eligible for randomization. The trained site staff will then conduct the following procedures:
 - Enter subject information into Interactive Web Randomization System (IWRS) to determine randomization code and kit number.
 - Explain the method of IP administration. Evaluate the subject's instillation technique.
 - Dispense 2 double-masked IP kits (sufficient for up to 10 days) to the subject to take home.
 - Observe as the subject self-administers the first dose of double-masked IP at the clinic/site. All remaining doses will be administered by the subject at home, OU BID (morning and evening, instillations approximately 8-12 hours apart).

- Drop comfort assessment
- Issue AT diary and train subject in diary completion.
- Dispense preservative-free AT (Refresh Plus[®]) and counsel subject to limit AT use to ≤ 2 instillations per day.

7.1.3 **Visit 3 (Day 7 \pm 2 days)**

The following procedures will be performed at Visit 3:

- Update CMs
- Assess AEs
- Administer the following subject-rated symptom assessments:
 - BCVA
 - Biomicroscopy and external eye exam
 - SE tear collection under slit lamp for biomarker test (quantitative POC MMP-9)
 - CFS
 - IOP
 - Collect AT diary and all used and unused AT and IP.
 - Issue new AT diary.
 - Dispense preservative-free AT (Refresh Plus[®]) and remind subject to limit AT use to ≤ 2 instillations per day.
 - Dispense 2 double-masked IP kits (sufficient for up to 10 days) to the subject to take home.

7.1.4 **Visit 4 (Day 14 \pm 2 days)**

The following procedures will be performed at Visit 4:

- Update CMs
- Assess AEs
- Administer the following subject-rated symptom assessments:
 - BCVA
 - Biomicroscopy and external eye exam
 - SE tear collection under slit lamp for biomarker test (quantitative POC MMP-9)
 - CFS

- IOP
- Collect AT diary and all used and unused AT and IP.
- Issue new AT diary.
- Dispense preservative-free AT (Refresh Plus[®]) and remind subject to limit AT use to ≤ 2 instillations per day.
- Dispense 4 double-masked IP kits (sufficient for up to 20 days) to the subject to take home.

7.1.5 **Visit 5 (Day 28 \pm 2 days)**

The following procedures are to be performed at Visit 5:

- Update CMs
- Assess AEs
- Administer the following subject-rated symptom assessments:
 - BCVA
 - Biomicroscopy and external eye exam
 - SE tear collection under slit lamp for biomarker test (quantitative POC MMP-9)
 - CFS
 - IOP
- Collect AT diary and all used and unused AT and IP.
- Issue new AT diary.
- Dispense preservative-free AT (Refresh Plus[®]) and remind subject to limit AT use to ≤ 2 instillations per day.
- Dispense 7 double-masked IP kits (sufficient for up to 35 days) to the subject to take home.
- Dosing and drop comfort assessment will take place **in clinic** at Visit 6. Advise subject to withhold 1 dose of IP on the day of Visit 6.

7.1.6 **Visit 6 (End of Study/Early Termination, Day 60 \pm 3 days)**

The following procedures are to be performed at the End of Study visit:

- Update CMs
- Assess AEs
- Administer the following subject-rated symptom assessments:
 - UPT for WOCBP*

- Safety labs: blood samples for chemistry and hematology*
- BCVA
-
- Biomicroscopy and external eye exam
- SE tear collection under slit lamp for biomarker test (quantitative POC MMP-9)
- CFS
 - **Note:** After CFS grading, wait at least 15 minutes before conducting
-
- IOP
- Dilated ophthalmoscopy
- IP administration and drop comfort assessment
- Collect AT diary and all used and unused AT and IP.

7.1.7 Unscheduled Visits

At times outside of normally scheduled visits, assessments will be conducted at the discretion of the Investigator.

7.1.8 Early Termination

In the event that a subject exits or is terminated from the study prior to the End of Study visit (Visit 6), every attempt will be made to ensure that all Visit 6 assessments are performed prior to the subject being discharged.

8. Study Assessments

The Schedule of Procedures and Assessments ([Appendix 1](#)) provides a list of study assessments and evaluations to be performed and the timing of each.

8.1 Efficacy Evaluations

Efficacy assessments will be conducted at the time points indicated on the Schedule of Procedures and Assessments ([Appendix 1](#)).

- tCFS (mNEI scale, 0-20) ([Appendix 3](#))

8.2 Safety Evaluations

Safety assessments will be performed at the time points indicated on the Schedule of Procedures and Assessments ([Appendix 1](#)).

- AE monitoring ([Section 8.2.1](#))
- Safety labs (chemistry and hematology) ([Section 8.2.2](#))
- BCVA ([Appendix 9](#))
- Slit lamp biomicroscopy and external eye exam ([Appendix 10](#))
- IOP ([Appendix 11](#))
- Dilated ophthalmoscopy ([Appendix 12](#))
- Drop comfort assessment ([Appendix 13](#))

8.2.1 Adverse Events (AEs) and Serious Adverse Events (SAEs)

Adverse events will be monitored throughout the study. Subjects will be encouraged to report any adverse findings during the study whether or not they are related to IP. These can be collected either in an unsolicited fashion without any prompting or in response to a general question such as: "Have you noticed anything different since you started the study; began the IP, etc.?"

All AEs will be captured on the appropriate case report form (CRF). Information to be collected at minimum includes event description, onset, assessment of severity, relationship to IP, and outcome.

The Investigator will record all AEs with start dates occurring any time after informed consent is obtained until 7 (for nonserious AEs) or 30 days (for SAEs) after the last day of study participation. At each study visit, the Investigator will inquire about the occurrence of AE/SAEs since the last visit. Events will be followed for outcome information until resolution or stabilization.

Any medical condition that is present at the time that the subject is screened will be considered baseline and not reported as an AE. However, if the subject's condition deteriorates at any time during the study, it will be recorded as an AE.

8.2.1.1 Definitions

An AE is any untoward medical occurrence in a clinical study participant, temporally associated with the use of study intervention, whether or not considered related to the study intervention. An AE can therefore be any unfavorable and unintended sign (including an abnormal laboratory finding), symptom, or disease (new or exacerbated) temporally associated with the use of study intervention.

An AE or suspected adverse reaction is considered "serious" if, in the view of either the Investigator or Sponsor, it results in any of the following outcomes:

- Death
- A life-threatening AE
- Inpatient hospitalization or prolongation of existing hospitalization
- A persistent or significant incapacity or substantial disruption of the ability to conduct normal life functions, or
- A congenital anomaly or birth defect

Important medical events that may not result in death, be life-threatening, or require hospitalization may be considered serious when, based upon appropriate medical judgment, they may jeopardize the subject and may require medical or surgical intervention to prevent one of the outcomes listed in this definition.

8.2.1.2 Classification of Adverse Events

Severity of Adverse Events

The severity of all AEs will be assessed by the Investigator and graded as follows:

- **Mild:** requires minimal or no treatment and do not interfere with the subject's daily activities
- **Moderate:** results in a low level of inconvenience or concern and may cause some interference with functioning

- **Severe:** interrupts a subject's usual daily activity and may require systemic drug therapy or other treatment. Severe events are usually potentially life-threatening or incapacitating. The term "severe" does not necessarily equate to "serious."

Relationship of Adverse Events

All AEs must have their relationship to study intervention assessed by the Investigator who examines and evaluates the subject based on temporal relationship and his/her clinical judgment. The degree of certainty about causality will be graded using the categories below. In a clinical study, the IP must always be suspect.

- **Unrelated:** no reasonable possibility that the administration of the IP caused the event, no temporal relationship between the IP and event onset, or an alternate etiology has been established
- **Related:** is known to occur with the IP, is a reasonable possibility that the IP caused the AE, or there is a temporal relationship between the IP and event. Reasonable possibility means that there is evidence to suggest a causal relationship between the IP and the AE.

Expectedness

An AE or suspected adverse reaction is considered "unexpected" if it is not listed in the Investigator's Brochure (IB), package insert, or device labeling or is not listed at the specificity or severity that has been observed; or, if an IB is not required or available, is not consistent with the risk information described in the protocol, as amended. "Unexpected," as used in this definition, also refers to AEs or suspected adverse reactions that are mentioned in the IB, package insert, or device labeling as occurring with a *class of drugs* (or other medical products) or as anticipated from the pharmacological properties or other characteristics of the IP, but are not specifically mentioned as occurring with the particular IP under investigation.

The Investigator will be responsible for determining whether an AE is unexpected, i.e., if the nature, severity, or frequency of the event is not consistent with the risk information previously described for the IP.

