8.2.1.3 Adverse Event Reporting Requirements

According to federal regulations, an Investigator must immediately report (within 24 hours) to the Sponsor any SAE, whether or not considered drug related, including those listed in the protocol or IB, and must include an assessment of whether there is a reasonable possibility that the drug caused the event. Study endpoints that are SAEs (e.g., all-cause mortality) must be reported in accordance with the protocol unless there is evidence suggesting a causal relationship between the drug and the event (e.g., death from anaphylaxis). In that case, the Investigator must immediately report the event to the Sponsor (See 21 Code of Federal Regulations [CFR] 312.64(b)).

According to federal regulations, the Sponsor must notify the US Food and Drug Administration (FDA) and all participating Investigators as soon as possible, but in no case later than 15 calendar days after the Sponsor determines that a potential serious risk arising from a clinical study qualifies for reporting. The Sponsor must report any suspected adverse reaction that is both serious and unexpected. The Sponsor must report an AE as a suspected adverse reaction only if there is evidence to suggest a causal relationship between the drug and the adverse event (See 21 CFR 312.32(c)(1)).

Furthermore, the Sponsor must also notify FDA of any unexpected fatal or life-threatening suspected adverse reaction as soon as possible but in no case later than 7 calendar days after the Sponsor's initial receipt of the information (See 21 CFR 312.32(c)(2)).

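### The Related and Unrelated causality definitions overlap with no rule of precedence, so the related-AE tables cannot be read as drug-attributed events

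*Protocol*

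**What the plan says.** **Definitions.** Protocol 8.2.1.2 (Relationship of Adverse Events) gives two categories.

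- *Related* has three alternatives: the event is a recognised effect of the product, there is a reasonable possibility that the product caused it, "or there is a temporal relationship between the IP and event".
- *Unrelated* also has three. The first two read "no reasonable possibility that the administration of the IP caused the event, no temporal relationship between the IP and event onset". The third is that the event has been shown to have another cause.

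The relationship is to be "assessed by the Investigator who examines and evaluates the subject based on temporal relationship and his/her clinical judgment". A closing sentence defines one of the Related alternatives: "Reasonable possibility means that there is evidence to suggest a causal relationship between the IP and the AE". SAP 9.5.1.4.1 repeats both category definitions and adds no order of precedence.

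**Neighbouring sections.** Protocol 8.2.1.1 opens with "An AE is any untoward medical occurrence in a clinical study participant, temporally associated with the use of study intervention", and adds that this holds whether or not the event is thought related. Under Protocol 8.2.1.3 the sponsor reports an AE as a suspected adverse reaction "only if there is evidence to suggest a causal relationship between the drug and the adverse event".

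**Where the category is used.** Protocol 9.4.3.1 plans a separate summary of AEs that the investigator reports as related. SAP 9.7.1.6.1 plans an overall summary by worst relationship and a table by system organ class, preferred term and maximum relationship. It presents a missing relationship as Related.

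**The concern.** A two-category causality scale is useful only if each event belongs to one category and the label means what the table title says. Here timing alone earns the Related label, yet timing is already built into the definition of an AE. With twice-daily dosing over 60 days, an event that starts on treatment will ordinarily have a temporal relationship to a dose. If the same event has an established other cause, it also satisfies Unrelated, and the investigator has no written basis for choosing.

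Ocular safety is part of the primary objective (Protocol 2.1), so these are not incidental outputs. A reader will take the related-AE tables to show what the drug did. Applied to the letter, the definition makes them nearly a copy of the table of all treatment-emergent AEs (TEAEs). Applied otherwise, they reflect each investigator's unrecorded choice between two definitions that both fit.

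**Working it through.** The documents give no figure to reproduce. The check is logical.

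**Step 1. Attributes taken from Protocol 8.2.1.2.** K = recognised effect of the product; R = reasonable possibility of causation; T = temporal relationship; A = another cause established. Each is yes or no, giving 2 × 2 × 2 × 2 = 16 patterns.

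**Step 2. The rules as written.**

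- Related = K or R or T
- Unrelated = (not R) or (not T) or A

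**Step 3. Count the patterns.**

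| | Both | Related only | Unrelated only | Neither |
|---|---|---|---|---|
| T = yes (8 patterns) | 6 | 2 | 0 | 0 |
| T = no (8 patterns) | 6 | 0 | 2 | 0 |
| All 16 | 12 | 2 | 2 | 0 |

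With T = yes, every pattern is Related. Unrelated also holds whenever R = no (4 patterns) or when R = yes and A = yes (2 patterns), so 4 + 2 = 6 overlap. Only R = yes with A = no escapes (2 patterns). No pattern with a temporal relationship is Unrelated only. With T = no, every pattern is Unrelated, and the 6 with K or R also meet Related.

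**Step 4. A plain example.** Take an on-treatment event with an established other cause, no reasonable possibility that the drug caused it, and not a recognised effect: K = no, R = no, T = yes, A = yes. It is Related through T, and Unrelated through both R = no and A = yes.

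**Step 5. Compare with the reporting standard.** Protocol 8.2.1.3 asks for evidence of causation. In 8.2.1.2 that requirement defines only the R alternative. An event with T = yes and R = no can be recorded as Related without meeting it, so the two sections attach different meanings to drug-attributed.

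**Step 6. Test the repair.** Let Related = T and (K or R), and suppose, for illustration, that an established other cause places the event in Unrelated. If the Unrelated list is otherwise left as it is, one pattern still meets both: K = yes, R = no, T = yes, A = no. If Unrelated is instead defined as every AE that is not Related, 3 patterns are Related (T = yes, A = no, with K or R), 16 − 3 = 13 are Unrelated, and none is both.

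**The case against.** **The investigator's judgment resolves it.** The assessment rests on clinical judgment as well as timing, and Protocol 8.2.1.1 treats timing and relatedness as distinct ideas. Neither document says that any onset after the first dose is a temporal relationship, and the TEAE window runs to 30 days after the last dose. This shows that the authors probably did not intend timing to decide the matter. It does not say which category applies when both definitions are met.

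**Leaning toward attribution is a deliberate, cautious choice.** The protocol says the product must always be under suspicion, and the SAP counts a missing relationship as Related. A low threshold is a legitimate policy, but it would need to say that Related prevails. The text instead makes an established other cause sufficient for Unrelated.

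**The pattern count is not an event count.** Correct. Some patterns, such as a reasonable possibility without any temporal relationship, are implausible. The count shows that the rule is ambiguous, not how often the ambiguity will arise.

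Three stronger readings are tempting, and the documents do not support them.

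- *The related-AE table cannot be interpreted at all.* Sponsor, subjects and site staff are masked (Protocol 5.3) and there is a randomized vehicle arm, so over-attribution should be similar across arms. A comparison between arms keeps meaning, and the all-causality TEAE tables in SAP 9.7.1.6.1 do not use the category.
- *Clearly unrelated serious events would be swept into causality-based reporting.* Protocol 8.2.1.3 sends every SAE to the sponsor whatever its relatedness, asks for a separate reasonable-possibility assessment, and requires evidence of causation for onward reporting of a suspected adverse reaction.
- *All TEAEs will be labelled Related.* That is only the upper bound under a literal reading. The documents give no basis for predicting the share or how it would vary by site.

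**Conclusion.** The point holds as a defect of definition. The two relationship categories are not mutually exclusive, no precedence is given in either document, and the Related category does not match the evidence standard in Protocol 8.2.1.3. The related-AE summary and the worst or maximum relationship tables therefore cannot be taken as a list of drug-attributed events.

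The extent is 12 of 16 logical patterns overall, and 6 of the 8 with a temporal relationship. This rests on reading the listed criteria as alternatives, as their wording indicates, and on on-treatment events ordinarily having a temporal relationship. Events recorded between consent and any dosing may lack one, but they are not TEAEs.

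The harm is confined to those descriptive tables. It should be corrected because the classification feeds planned safety outputs and the repair is cheap.

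**What to change.** Make the same change in Protocol 8.2.1.2 and SAP 9.5.1.4.1:

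1. Remove timing as a stand-alone criterion for Related. Require a temporal relationship together with either a recognised effect of the product or a reasonable possibility, the latter as already defined by evidence of causation. Keep the recognised-effect criterion; nothing here argues for dropping it.
2. Add one precedence sentence stating which category applies when another cause has been established.
3. Define Unrelated as every AE that does not meet Related, so that each AE falls in exactly one category.
4. Check that the result agrees with Protocol 8.2.1.3.

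The cost is a short rewording in each document and a reminder to sites. Attribution becomes slightly less inclusive, because timing alone no longer earns the Related label. No planned table has to be added or removed.
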